5.0 STUDY DESIGN

5.1 Discussion of Study Design

This will be a single-dose, randomized, open-label, four-way crossover, four-period, four-sequence, single-center, drug-drug interaction (DDI) study of generic formulation of Nifedipine extended-release tablets, 60 mg and reference listed drug PROCARDIA XL extended-release tablets, 60 mg with or without co-administration multiple-dose of PPI/antacid, omeprazole/sodium bicarbonate capsules 40 mg/1100 mg capsule under fasting conditions.

The generic nifedipine ER tablets based on a matrix design are available at only two strengths (30 and 60 mg), and the higher dose of 60 mg was chosen for its sensitivity of PK metrics in bioequivalence studies as per FDA guidance (Guidance for Industry: Bioequivalence studies with pharmacokinetic endpoints for drugs submitted under an ANDA, Dec 2013). The safety concern of administering 60-mg single-dose nifedipine is minimal, considering that the existing product-specific bioequivalence guidance recommends generic applicants to conduct fasting and fed single-dose crossover BE studies administering 90-mg nifedipine ER tablets in healthy volunteers. On the other hand, the higher dose of 40mg/1100mg omeprazole/sodium bicarbonate capsules between the two strengths (20 or 40 mg omeprazole) was selected for a more significant gastric pH elevation. Administering 40 mg omeprazole daily for 7 consecutive days in healthy volunteers should be considered safe as shown in the past clinical studies [12, 19, 20]. In addition, omeprazole/sodium bicarbonate at the lower strength (20 mg omeprazole) is an OTC product.

The products will be studied using a crossover design with 65-66 healthy, non-smoking male and non-pregnant female volunteers being administered an oral dose of 1 × 60 mg extended-release tablet with or without co-administration multiple-dose of omeprazole / sodium bicarbonate, 1 x 40 mg/1100 mg once daily for 7 consecutive days under fasting conditions (i.e. subjects are dosed every 24 hrs). There will be at least a 14-day washout after Nifedipine only dosing (Study arms A or B) and for Study arms C and D (e.g., omeprazole/sodium bicarbonate followed with Nifedipine), at least 14 days after the last dose with omeprazole/sodium bicarbonate until the next study arm dose. Blood samples will be collected at pre-dose (0 hour) and at 1, 2, 3, 4, 5, 6, 7, 8, 9, 10, 12, 16, 20, 24, 36, and 48 hours after nifedipine dosing for Study arm A and B on Day 2 and on Day 7 for Study arm C and D in each study period.

5.2 Study Duration and Confinement

Study arm A and B: Subjects will be confined to the clinic from at least 10 hours prior (e.g., 5 pm Friday) to dosing (e.g., 8:00 am Saturday) until at least 48-hours post-dose of nifedipine, for a total of at least 58 hours in each study period.

Study arm C and D:

Subjects will be confined to clinic from at least 1 hour prior to dosing omeprazole/sodium bicarbonate capsules on Day 1 and Day 2 and then the subjects will be discharged 1 hour post-dose.

Subjects will be returning to the clinic 1 hour prior to dosing on Day 3 and can check-in after dosing or may check-in the evening to be confined to the clinic until at least 48 hours post-dose (test and reference) nifedipine dosing on Day 7. Total confinement from Day 1 to Day 9 will be of at least 148 hours (approximately 6 days) in each study period.

This study will consist of four study periods with a washout period of at least 14 days after Nifedipine only dosing (Study arms A or B) and for Study arms C and D (e.g., omeprazole/sodium bicarbonate followed with Nifedipine), at least 14 days after the last dose with omeprazole/sodium bicarbonate until the next study arm dose. The total anticipated duration of the clinical part of the study will be approximately 9 weeks (since signing the ICF by the first subject up to the last planned study procedure of the last subject).

5.3 Randomization and Blinding

In this study, the assignment of study arm groups (randomization scheme) will be generated by a computer program designed and run in SAS[®] Version 9.4 [REDACTED]. This is an open-label study and subjects as well as clinic staff will not be blinded to the randomization. The bioanalytical laboratory will not have access to the randomization scheme until the bioanalytical analysis is complete.

Subjects who meet the eligibility criteria will be randomly assigned equally into one of the following four sequence groups:

	Period 1	Period 2	Period 3	Period 4
Sequence 1	A	B	C	D
Sequence 2	B	C	D	A
Sequence 3	C	D	A	B
Sequence 4	D	A	B	C

Each subject is scheduled to receive four periods by the end of the study (See Appendix A).

Study arm A (Test): Nifedipine extended-release tablets [REDACTED]
[REDACTED] 60 mg

Study arm B (Reference): PROCARDIA XL extended-release tablets [REDACTED]
60 mg

Study arm C (PPI/antacid + Test): omeprazole/sodium bicarbonate capsules, 40 mg/1100 mg + Nifedipine extended-release tablets [REDACTED],
[REDACTED], 60 mg.

Study arm D (PPI/antacid + Reference): omeprazole/sodium bicarbonate capsules, 40 mg/1100 mg + PROCARDIA XL extended-release tablets [REDACTED] 60 mg.

The trial will be performed as an open-label study as the pharmacokinetic profile should not be expected to be affected by having the knowledge of reference or generic nifedipine ER tablets was administered. Blinding of the subjects as well as clinic staff is not considered necessary. Only the bioanalytical laboratory staff will not have access to the randomization scheme until the bioanalytical analysis is complete.

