1.0 SYNOPSIS

Title:	A Single-Dose, Open-label, Randomized, Crossover, Drug-Drug Interaction Study of Nifedipine Extended-release Tablets with or without Multiple-dose Administration of Proton-pump inhibitor Omeprazole/sodium bicarbonate in Healthy Volunteers.
Objective:	The objective of this study is to compare pharmacokinetics of nifedipine from both generic Nifedipine oral extended-release tablets, 60 mg and reference listed drug PROCARDIA XL (nifedipine; RLD) extended-release tablets, 60 mg when co-administered with or without proton pump inhibitor (PPI)/antacid, omeprazole/sodium bicarbonate 40 mg/1100 mg capsules in healthy males and non-pregnant females under fasting conditions, whose gastric pH will be measured by SmartPill™ technology.
Experimental Design:	A single-dose, randomized, open-label, drug-drug interaction (DDI), 4-way crossover, four-treatment, four-sequence, bioequivalence study.
Study Rationale:	This is an in vivo study to evaluate the test and RLD formulation pharmacokinetics of nifedipine when co-administered with or without PPI/antacid. The outcome of this study will help the Agency advance further understanding about product PK performance of nifedipine in potential patient population co-administered with PPI or with abnormal gastric pH and improve review standards for equivalence of this category of oral ER products if necessary.
Study Population:	65-66 subjects will be enrolled (minimum of 52 subjects to complete the study). The subjects will be dosed in two or more groups. Healthy, non-smoking male and non-pregnant female volunteers, 18-55 years of age, with a body mass index (BMI) within 18.5-35.0 kg/m ² , inclusive.
Test Drug:	Nifedipine extended-release tablets, 60 mg [REDACTED]
Reference Drug:	PROCARDIA XL extended-release tablets, 60 mg [REDACTED]
PPI/antacid:	omeprazole/sodium bicarbonate 40 mg/1100 mg capsule
Study arm A (Test Drug):	1 x 60 mg Nifedipine extended-release tablet
Study arm B (Reference Drug):	1 x 60 mg PROCARDIA XL (nifedipine) extended-release tablet
Study arm C (PPI/ antacid + Test Drug)	1 x 40 mg/1100 mg omeprazole/sodium bicarbonate capsule daily over a period of 7 days + 1 x 60 mg Nifedipine extended-release tablet on day 7
Study arm D (PPI/ antacid + Reference Drug)	1 x 40 mg/1100 mg omeprazole/sodium bicarbonate capsule daily over a period of 7 days + 1 x 60 mg PROCARDIA XL (nifedipine) extended-release tablet on day 7

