3.2 Rationale

The current research proposal is funded by the FDA via a contract agreement (HHSF 22320161004I) with the purpose of investigating the in vivo performance consistency of oral MR drug products under the effect of an elevated gastric pH environment (e.g. co-administration of PPIs). We have chosen to focus on nifedipine ER tablets (brand name and generic products) because the RLD is an osmotic pump and there is a generic version commercially available as matrix-based formulations. We will evaluate the bioequivalence in an open label, clinical study with and without multiple-dose PPI co-administered with the brand name drug and a generic version. In the current study, clearance, volume of distribution, and absorption, as determined by physiological variables (e.g. gastric emptying, motility, pH), are assumed to have less inter-occasion variability compared to the variability arising from formulation performance within the same subject [6, 12-14]. Therefore, differences between two products because of formulation factors can be determined [15].

This clinical study will be open-label because blood concentration levels cannot be influenced by knowledge of the identity of treatment, however, the laboratory analysts will be unaware of the study product sequences. The period of 48 hours, over which blood samples will be collected, is considered to be sufficiently long to adequately characterize the concentration-time profile of extended-release nifedipine (the mean half-life of nifedipine is less than 10 hours). It has been shown that administering multiple-dose (e.g. 7 days) PPIs (i.e. omeprazole) in healthy volunteers can effectively increase their gastric pH [16, 17]. In the current clinical study, subjects will be dosed with PPIs in the first two days without confinement (i.e. outpatient visits) to reduce their burden. Dosing the subjects with PPIs in confinement for the last 5 days is deemed necessary in order to standardize the food effect (omeprazole administration under fasting conditions) prior to the PK study of nifedipine ER tablets. Since the omeprazole PD effect can be eliminated after 3-5 days of discontinuing the drug, a wash-out period of at least 7 days is sufficient to allow the complete elimination of the drug before subsequent dosing and to avoid carry-over effects. In this study, a wash-out period of at least 14 days is chosen to ensure the scientific and logistic conduct of the study.

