4.0 STUDY OBJECTIVE

4.1 Study Objective

The objective of this study is to compare pharmacokinetics of nifedipine from both generic Nifedipine oral extended-release tablets, 60 mg and reference listed drug PROCARDIA XL (nifedipine) extended-release tablets, 60 mg when co-administered with or without proton pump inhibitor (PPI)/antacid, omeprazole/sodium bicarbonate capsules 40 mg/1100 mg capsules in healthy males and non-pregnant females under fasting conditions.

The two one-sided t-tests procedure Schuirmann proposed will be used to construct the 90% confidence interval at the $\alpha=0.05$ level of significance for the ratio of geometric mean of PK parameters AUC_t, AUC_{inf} and C_{max}. The limits of the 90% confidence intervals are 80.00%-125.00% which will be used for the statistical hypothesis testing. Therefore, it consists of decomposing the interval hypotheses into two sets of one-sided hypotheses.

For the drug interaction for both test and reference products, the calculated 90% confidence interval (CI) for the ratios of geometric means for AUC_t, AUC_{inf} and C_{max} will be used for the following two PK comparisons to assess if the statistical significance of interaction effect between the product type effect (test or reference) and the effect of co-administrating PPI/antacid is or not.

- Test with PPI (Study Arm C)/Test without PPI (Study Arm A)
- Reference with PPI (Study Arm D)/Reference without PPI (Study Arm B)

Hypothesis 1.1: The hypotheses for testing of the interaction effect between Test product and the effect of co-administrating PPI/antacid are as follows:

- The null hypothesis (H01): there is statistical significance of the interaction effect if the 90% CI of the ratios of geometric means for AUC_t, AUC_{inf} and C_{max} is less than 80.00%.
- The alternative hypothesis (H11): there is no statistical significance of the interaction effect if the 90% CI of the ratios of geometric means for AUC_t, AUC_{inf} and C_{max} is greater than or equal to 80.00%.
- The null hypothesis (H02): there is statistical significance of the interaction effect if the 90% CI of the ratios of geometric means for AUC_t, AUC_{inf} and C_{max} is greater than 125.00%.

- The alternative hypothesis (H12): there is no statistical significance of the interaction effect if the 90% CI of the ratios of geometric means for AUC_t, AUC_{inf} and C_{max} is less than or equal to 125.00%.

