13.3.3 Statistical Analysis

Descriptive statistics (min, max, median, mean, standard deviation and coefficient of variability) of all PK parameters will be provided for nifedipine for all study arm groups.

ANOVA including sequence, subjects nested within sequence, period and study arm will be performed on the ln-transformed data for AUC_t , AUC_{inf} and C_{max} and on the untransformed data for T_{max} , λ and $T_{1/2}$.

T_{max} will be analyzed using an additional non-parametric test (Wilcoxon test).

The 90% CI of the ratios of geometric means for AUC_t , AUC_{inf} and C_{max} will be calculated based on the LSMEANS and ESTIMATE of the ANOVA.

The following PK comparisons will be carried out:

- Test with PPI (Study arm C)/Test without PPI (Study arm A)
- Reference with PPI (Study arm D)/Reference without PPI (Study arm B)
- Test with PPI (Study arm C)/Reference with PPI (Study arm D)
- Test without PPI (Study arm A)/Reference without PPI (Study arm B)

For Pharmacodynamic Data:

The descriptive statistics (min, max, median, mean, standard deviation and coefficient of variability) of the gastric pH and change of gastric pH will be calculated for both test and reference products.

Analysis of Variance (ANOVA) for gastric pH and change of gastric pH from baseline will be carried out.

The following gastric pH comparisons will be carried out:

- Study arm C PPI (Day7) – Study arm A (Day2)

- Study arm D_{PPI (Day7)} – Study arm B_(Day2)
- The comparison of the change between test and reference can be assessed

Additional statistical and alternate tests will be performed if necessary.

Missing data will not be included in the statistical analysis. There are potential two kinds of unbalanced designs for the analysis: (1) unequal number of subjects across groups, (2) missing cells: there are not available data for some subjects. The Type 3 method will be used for the calculation of sums of squares using SAS software. All the fixed effects will be tested using the Type 3 in the ANOVA to detect statistically significant differences ($\alpha=0.05$) if applicable. A mixed effects ANOVA model for gastric pH with fixed factors of sequence, period, and study arm and random effects of subject will be fit. A compound-symmetric or other appropriate covariance structure will be used in the analysis.

The null hypotheses for gastric pH comparisons for different study arms are:

- For the comparison of Study Arm A and Study Arm C

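### The four sequences are not balanced for preceding arm, so any PPI effect outlasting the washout would look like a product difference; a Williams square prevents this cheaply

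*Combined protocol and SAP*

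**What the plan says.** - **Sequences (5.3).** "Subjects who meet the eligibility criteria will be randomly assigned equally into one of the following four sequence groups". The table beneath lists ABCD, BCDA, CDAB and DABC.
- **PPI arms (Synopsis).** Arms C and D each include one "omeprazole/sodium bicarbonate capsule daily over a period of 7 days", with nifedipine on Day 7. Arms A and B have no PPI.
- **Washout (5.1).** After a PPI arm it is "at least 14 days after the last dose with omeprazole/sodium bicarbonate until the next study arm dose".
- **Justification (3.2).** "Since the omeprazole PD effect can be eliminated after 3-5 days of discontinuing the drug", at least 7 days is called sufficient "to allow the complete elimination of the drug before subsequent dosing and to avoid carry-over effects", and at least 14 days is used. On nifedipine itself, "the mean half-life of nifedipine is less than 10 hours".
- **Model (13.3.3).** "ANOVA including sequence, subjects nested within sequence, period and study arm will be performed on the ln-transformed data". No carryover term is listed. The four planned ratios are C/A, D/B, C/D and A/B.

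The documents give no reason for choosing this particular set of sequences.

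**The concern.** The only successions in the four sequences are A-B, B-C, C-D and D-A, three times each. The other eight ordered pairs never occur. Each arm therefore has a single possible predecessor, and the two arms that follow a PPI arm (A and D) belong to different products. A residual PPI effect would reach test without PPI but not reference without PPI. If it acted in PPI arms too, it would reach reference with PPI but not test with PPI. Either way it would resemble a formulation difference.

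That is the question the trial was built to answer: Section 4.1 frames the drug-interaction aim as an interaction between product type and PPI co-administration. The washout is the only protection against this, although the layout could supply a second one.

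**Working it through.** The plan gives no carryover figure to reproduce. Its only related figures are the durations in 3.2 and 5.1: 14/5 = 2.8 and 14/3 = 4.7, so the washout is about three to five times the stated PPI effect. For nifedipine, 14 days is 336 hours, or more than 336/10 = 33 half-lives. Only a residual PPI effect matters here.

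**Setup.** Let d be the residual effect on ln(PK) in the period after a PPI arm. With equal sequence sizes and complete data, arms are orthogonal to subjects and periods. The bias in an arm mean is then d times the share of its four positions that follow a PPI arm.

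| Arm | Cyclic (5.3) | Williams (ABDC, BCAD, CDBA, DACB) |
|---|---|---|
| A | 3/4 (after D, three times) | 2/4 (after C, D) |
| B | 0 | 2/4 (after D, C) |
| C | 0 | 1/4 (after D) |
| D | 3/4 (after C, three times) | 1/4 (after C) |

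The loading is 3/4 and not 1 because each arm is first in one sequence. If the residual acts only in arms without PPI, set the C and D rows to 0. Differencing gives the bias in units of d:

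| Contrast | Cyclic, all arms | Cyclic, A and B only | Williams, all arms | Williams, A and B only |
|---|---|---|---|---|
| A/B | +0.75 | +0.75 | 0 | 0 |
| C/D | -0.75 | 0 | 0 | 0 |
| C/A | -0.75 | -0.75 | -0.25 | -0.50 |
| D/B | +0.75 | 0 | -0.25 | -0.50 |
| (C/A)/(D/B) | -1.50 | -0.75 | 0 | 0 |

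A least-squares fit of the subject, period and arm model with 13 subjects per sequence (52 in all) returns the same values.

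**Size.** The documents give no residual, so d is an assumption. The spurious ratio is exp(multiplier × d):

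| d (assumed) | A/B, cyclic | (C/A)/(D/B), cyclic, A and B only | (C/A)/(D/B), cyclic, all arms |
|---|---|---|---|
| 0.01 | 1.008 | 0.993 | 0.985 |
| 0.02 | 1.015 | 0.985 | 0.970 |
| 0.05 | 1.038 | 0.963 | 0.928 |

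For scale, Section 3.1 cites an AUC ratio of 1.26 for an immediate-release tablet under full PPI effect, and ln 1.26 = 0.231. A d of 0.05 would need 0.05/0.231 = 22% of that effect to persist through the washout. The cited Cmax ratio is 0.87, so for Cmax the signs could reverse.

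**Precision.** Without a carryover term, every pairwise contrast has variance 2.0 σ²/n in both squares. A single carryover term raises it to (2.0 + b²v) σ²/n. Here b is the multiplier above and v = 4/R, where R is the sum of squares of the carryover indicator left after subject, period and arm, per four subjects.

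- Cyclic, all arms: R = 3.75 - 0.25 - 0.75 - 2.25 = 0.5, v = 8, variance 2.0 + 0.5625 × 8 = 6.5.
- Williams, all arms: R = 3.75 - 0.25 - 0.75 - 0.25 = 2.5, v = 1.6, C/A and D/B variance 2.0 + 0.0625 × 1.6 = 2.1.
- Williams, A and B only: R = 3 - 0.5 - 0.5 - 1 = 1, v = 4, C/A and D/B variance 2.0 + 0.25 × 4 = 3.0.
- Full first-order carryover (one term per preceding arm): 11.0 cyclic, 2.2 Williams.

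With the planned CV of 27% (7.1), σ² = ln(1 + 0.27²) = 0.0704. At 52 completers and the all-arms term, the standard error of d is √(8 × 0.0704/52) = 0.10 in the cyclic square and √(1.6 × 0.0704/52) = 0.047 in the Williams square.

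**The case against.** The strongest reply is that the washout already deals with carryover. Section 3.2 addresses it directly, and nothing in the documents suggests that d differs from zero. This stands, and it limits the weight of the point.

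A second reply concerns arm D, which has its own seven days of PPI. Its nifedipine dose falls at least 14 + 6 = 20 days after the previous PPI dose (23 days in the Appendix A example, Day 43 to Day 66). A leftover adding fully to a renewed course is hard to credit. This also stands. A reader might infer from the sequence table that all four planned ratios are biased, but if the residual acts only in A and B, C/D and D/B are unbiased and the product-by-PPI bias halves.

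A reader might also infer that carryover cannot be checked in this layout. It can be estimated, though imprecisely. Gastric pH is also measured in every period (8.4), and 13.3.3 plans an A-versus-B pH comparison, which bears on residual pH elevation although it is not labelled a carryover check. The 5%-of-Cmax pre-dose rule in 13.3.1 does not help, because it detects residual nifedipine only.

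Finally, the Williams square is not free of bias. If the residual acts only in A and B, D/B worsens from 0 to -0.5d under the unchanged ANOVA, while C/A improves only from -0.75d to -0.5d. What survives is that this bias is equal for both products and so cannot create a false product difference.

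**Conclusion.** The concern holds as a cheap improvement to the design. The predecessor imbalance is plain from the sequence table. Conditional on a residual PPI effect d, A/B is biased by +0.75d and C/A by -0.75d whether or not the residual acts in arm D. C/D (-0.75d) and D/B (+0.75d) are affected only if it does. The product-by-PPI contrast is biased by -0.75d to -1.5d; it is not among the four listed ratios but follows from comparing two of them.

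The documents do not support reading this as a bias that has occurred or is likely, given a washout of about three to five times the stated effect duration. The multipliers assume a first-order residual of the same size after C and D, equal sequence sizes and complete data. An enrolment of 65-66 cannot be split exactly into four, so they are very slightly approximate under either square.

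**What to change.** If dosing has not begun, replace the four sequences in 5.3 with a Williams square, for example ABDC, BCAD, CDBA, DACB, in which each arm follows every other arm exactly once. Four periods, four sequences, washout, dosing, primary ANOVA and contrast variance are unchanged.

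Add to 13.3.3 a prespecified sensitivity analysis with a carryover term. It removes the bias left in C/A and D/B when the term matches the way the residual acts, and raises their variance from 2.0 to between 2.1 and 3.0 σ²/n depending on the carryover model, against up to 11.0 in the present square.

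The cost is a new sequence table and randomization list, plus resubmission as a design change (15.1) to the two boards named in 14.2. No subjects, visits or procedures are added.

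If dosing has begun, keep the sequences, state the limitation in the report, and prespecify the comparison of gastric pH in A against B, outside Period 1, as a check for residual PPI effect.
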